9.3 Populations for analyses

Definitions of the analysis sets for each outcome variable are provided in Table 12.

Table 12 Summary of outcome variables and analysis populations

Outcome variable	Populations
Efficacy Data	
PFS, 6mPFS, 12mPFS	Safety analysis set
OS, 6mOS, 12mOS, 18mOS,	Safety analysis set
ORR, PROs, and symptom endpoints	Safety analysis set
DoR	Responders analysis set
TTD	Safety analysis set
PRO	Safety analysis set
Hospital resources	Safety analysis set
Demography	Safety analysis set
Biomarkers	Biomarkers Analysis Evaluable Set
Safety Data	
Exposure	Safety analysis set
AEs	Safety analysis set
Laboratory measurements	Safety analysis set
Vital Signs	Safety analysis set

AE Adverse event; XmPFS Proportion of patients alive and progression free at X months from inclusion; XmOS Proportion of patients alive X months from inclusion; ITT Intent-to-treat population; ORR Objective response rate; OS Overall survival; PFS Progression-free survival; DoR Duration of Response; TTD Time to Treatment Duration; PRO Patient-reported outcome.

9.3.1 Safety analysis set

The safety analysis set will include all included patients that received at least one dose of study treatment. Safety, efficacy, and PROs data will be summarized using the safety analysis set. (Patients who were enrolled but did not subsequently go on to receive study treatment will not be included in the analysis.)

Responders Analysis Set: The subset of patients, within the Safety Analysis Set who are evaluable for response analysis and who achieve an objective response.

9.3.2 Biomarker analysis evaluable population

The Biomarker analysis set (BAS) will consist of all patients who received at least 1 dose of study treatment and for whom tumor and/or blood samples are available.

9.4 Outcome measures for analyses

AE: Number and proportion of patients with AEs in total and by causality and severity

AE: Number and proportion of patients with Grade 3 and Grade 4 AEs in total and by causality

SAE: Number and proportion of patients with SAEs in total and by causality and severity

AEs leading to death: Number and proportion of patients with AEs leading to death

AEs leading to treatment interruption or discontinuation: Number and proportion of patients with AEs leading to treatment interruption and/or discontinuation

AESI: Defined as an AE of scientific and medical interest specific to understanding of the IP. AESIs for durvalumab include, but are not limited to, events with a potential inflammatory or immune-mediated mechanism and which may require more frequent monitoring and/or interventions such as steroids, immunosuppressants, and/or hormone replacement therapy. In order to further characterize safety objectives related to AESIs, outcome measures will be assessed, which may include (and are not necessarily limited to) the following:

- (a) Number and proportion of patients with AESIs, by predefined type (or newly defined by this study) in total and by seriousness, severity and causality, including immune-relatedness;
- (b) Number and proportion of patients who received steroids, immunosuppressants, and/or hormone replacement therapy to manage AESIs;
- (c) Time from start of durvalumab to the onset of an AESI predefined type, all interventions of AESIs by type of intervention (including intervention with steroids, immunosuppressants, and/or hormone replacement therapy), and time from onset of an AESI type to resolution;
- (d) Duration of the intervention with steroids, immunosuppressants, and/or hormone replacement therapy until the resolution of AESI;
- (e) Laboratory findings, vital signs, and other safety parameters associated with AESIs will be summarized as part of the AESI outcome measures.

imAE: The imAEs will be assessed as a subset of AESIs. An imAE is defined as an AESI that is associated with drug exposure and is consistent with an immune-mediated MOA and where there is no clear alternate etiology.

PFS: Defined as the time from the first date of treatment until the date of objective disease progression or death (by any cause in the absence of progression) regardless of whether the patient withdraws from IP or receives another anticancer therapy prior to progression.

PFS (days) = Date of event or Censor date – treatment start date +1

Patients who have not progressed or died at the time of analysis will be censored at the time of the latest date of assessment from their last evaluable assessment. However, if the patient progresses or dies after 2 or more missed visits, the patient will be censored at the time of the latest evaluable assessment prior to the 2 missed visits. If the patient has no evaluable visits or does not have baseline data, he/she will be censored at Day 1 unless he/she dies within 2 visits of baseline, in which case the date of death is the event date.

OS: Defined as the time from the first date of treatment until death due to any cause.

OS (days) = Death date or Censor date - treatment start date +1

Any patient not known to have died at the time of analysis will be censored based on the last recorded date on which the patient was known to be alive.

ORR: Based on Investigator–assessed response to treatment of CR and PR, per RECIST1.1.

DoR: Defined as the time from the date of first documented response per RECIST1.1 until the first date of documented progression per RECIST1.1 or death in the absence of disease progression.

DoR (days) = Date of PFS event or censoring – Date of first response +1

The end of response should coincide with the date of progression or death from any cause used for the PFS endpoint. If a patient does not progress following a response, then the patients' DoR will be censored at the PFS censoring time. DoR will not be defined for those patients who do not have a documented response.

Time to symptom deterioration (EORTC QLC-C30 and QLC-LC13): Defined as the time from start of study drug until the date of the first clinically meaningful symptom deterioration that is confirmed at the subsequent assessment or death (by any cause) in the absence of a clinically meaningful symptom deterioration, regardless of whether the patient withdraws from study drug or receives another anticancer therapy prior to symptom deterioration.

Change from baseline (EORTC QLC-C30 and QLC-LC13, PRO-CTCAE): Defined as the post-treatment value minus the value at baseline. The % change from baseline will be calculated as (postbaseline value - baseline value) / baseline value x 100.

Treatment duration: Defined as Treatment end date - Treatment start date +1; will be summarized.

In addition, demographics, medical history, comorbidities, extent of disease at diagnosis (eg, stage and histology) will be reported. Specific details of planned analyses will be described in the SAP.

Use of resources: To describe health care resources use related to management of ES-SCLC patients treated with durvalumab in combination with platinum–etoposide as first-line treatment. Description will include:

- (a) Number of hospitalizations
- (b) Length of hospitalizations: time from date of admission to discharge date
- (c) Number of visits to oncology service
- (d) Number of emergency visits
- (e) Number of outpatient visits
- (f) Number of imaging tests
- (g) Number of biopsy-related procedures
- (h) Treatment dose, duration, number of cycles

9.5 Statistical analyses

Analyses will be performed by AstraZeneca or its representatives. A comprehensive statistical analysis plan will be developed and finalized within 3 months of the first enrolled patient and will describe the patient populations to be included in the analyses, and procedures for accounting for missing, unused, and spurious data.

Descriptive statistics will be used for all variables, as appropriate. Continuous variables will be summarized by the number of observations (n), mean, standard deviation, median, quartiles (Q1 and Q3), minimum, and maximum. Categorical variables will be summarized by frequency counts and percentages for each category.

For all summaries of AEs, only treatment-emergent AEs will be included. Treatment-emergent AEs are defined as events present at baseline that worsen in intensity after administration of IP or events absent at baseline that emerge after administration of IP, for the period extending to 90 days after the last dose of IP. Baseline will be the last assessment of the variable under consideration prior to the first IP dose administration.

9.5.1 Analysis of the primary variables

Safety data will be summarized descriptively overall, by seriousness, by causality, and by maximum NCI CTCAE Grade. The exact 95% CIs around the incidence of Grade 3 and Grade 4 PRAEs will be reported. All outputs will be summarized for the safety analysis test.

A subgroup analysis may be conducted in the following subgroups, assuming sufficient sample size per subgroup: platinum therapy receiving (carboplatin or cisplatin), age, gender, performance status, smoking status and CNS metastasis at baseline (Y/N).

9.5.2 Analysis of the secondary variables

9.5.2.1 Safety variables

Adverse events

Total SAEs, AESIs, AEs leading to death, and AEs leading to study drug interruption or discontinuation will be summarized by Medical Dictionary for Regulatory Activities (MedDRA) by system organ class and preferred term, causality, and maximum NCI CTCAE Grade. Deaths from all causes will be also summarized.

Data from all cycles of will be combined in the presentation of safety data. AEs (both in terms of MedDRA preferred term and CTCAE grade) will be listed individually by patient. Any AE occurring before treatment with IP will be included in the data listings but will not be included in the summary tables of AEs. Any AE occurring within 90 days of discontinuation of IP may be included in the AE summaries, but the majority of the AE summaries will omit the AEs observed after a patient has received further therapy for cancer. Further details will be provided in the SAP. Any AE that occurs after a patient has received further therapy for cancer (following discontinuation of IP) will be flagged in the data listings.

For the change from baseline summaries for vital signs, laboratory data, ECGs, and physical examination, the baseline value will be the latest result obtained prior to the first IP dose administration.

The QTcF will be derived during creation of the reporting database using the reported ECG values (RR and QT) using the following formula:

$$QTcF = QT/RR^{(1/3)} \text{ where RR is in seconds}$$

Corrected calcium product will be derived during creation of the reporting database using the following formula:

$$\text{Corrected calcium (mmol/L)} = \text{Total calcium (mmol/L)} + ([40 - \text{Albumin (G/L)}] \times 0.02)$$

The denominator used in laboratory summaries will include only evaluable patients, ie, those who had sufficient data to have the possibility of an abnormality, for example:

- If a CTCAE criterion involves a change from baseline, evaluable patients would have both a predose and at least 1 postdose value recorded.
- If a CTCAE criterion does not consider changes from baseline, to be evaluable, the patient need only have 1 postdose value recorded.

The denominator in vital signs data should include only those patients with recorded data.

9.5.2.2 Efficacy variables

Efficacy data will be reported for patients overall. Results of all statistical analysis will be presented using a 95% confidence interval (CI), unless otherwise stated.

The following table (Table 13) details which endpoints are to be subjected to statistical analysis.

Table 13 Pre-planned statistical and sensitivity analyses to be conducted

Endpoints analyzed	Notes
Progression-free survival	Analysis by Kaplan Meier estimates using Investigator RECIST 1.1 assessments
Objective response rate	Analysis using Investigator RECIST 1.1 assessments
Duration of response	Analysis by Kaplan Meier estimates using Investigator RECIST 1.1 assessments, in patients with documented response
PFS at 6 and 12 months	Using the Kaplan Meier estimates of progression free survival at 6 and 12 months
Overall survival	Analysis by Kaplan Meier estimates
Overall survival at 6, 12 and 18 months	Using the Kaplan Meier estimates of OS at 6, 12 and 18 months
Time to deterioration (EORTC QLQ-C30 and QLQ-LC13 endpoints)	Analysis by Kaplan Meier estimates. Change from baseline values will be calculated.

EORTC European Organisation for Research and Treatment of Cancer; QLQ-C30 v3 30-item Core Quality of Life Questionnaire, version 3; QLQ-LC13 13-item Lung Cancer Quality of Life Questionnaire;

RECIST 1.1 Response Evaluation Criteria in Solid Tumors, version 1.1.

Progression-free survival

The PFS analysis will be based on the programmatically derived RECIST 1.1 using the Investigator tumor assessments. The analysis will be performed using Kaplan Meier plots. Summaries of the number and percentage of patients experiencing a PFS event will be provided along with median PFS and its 95% confidence interval. In addition, the proportion of patients who are progression-free at 6 and 12 months will be presented.

A subgroup analysis may be conducted comparing PFS in the following subgroups, assuming sufficient sample size per subgroup: platinum therapy receiving (carboplatin or cisplatin), age, gender, performance status, smoking status and CNS metastasis at baseline (Y/N).

Other baseline variables may also be assessed if there is clinical justification. The purpose of the subgroup analyses is to assess the consistency of treatment effect across expected prognostic and/or predictive factors.

For each subgroup, the HR and 95% CI will be calculated by Cox regression and a log-rank test will be provided.

Objective response rate

The ORR will be based on the programmatically derived RECIST 1.1 using the investigator tumor data. Summaries will be produced that present the number and percentage of patients with a tumor response (CR/PR). 95% CI will also be presented.

Duration of response

DoR will be analyzed using the investigator tumor data in responding patients. Descriptive data will be provided for the DoR in responding patients, including the associated Kaplan-Meier curves.

Overall survival

OS will be analyzed using a Kaplan-Meier plots. Summaries of the number and percentage of patients who have died, those still in survival follow-up, those lost to follow-up, and those who have withdrawn consent will be provided along with the median OS and corresponding 95% CI. In addition, the proportion of patients alive at 6, 12, and 18 months will be presented.

A subgroup analysis may be conducted comparing OS in the following subgroups, assuming sufficient sample size per subgroup: platinum therapy receiving (carboplatin or cisplatin), age, gender, performance status, smoking status and CNS metastasis at baseline (Y/N).

For each subgroup, the HR and 95% CI will be calculated by Cox regression and a log-rank test will be provided.

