During the treatment period, patients who are clinically stable at an initial RECIST 1.1-defined PD may continue to receive study treatment at the discretion of the Investigator and patient. A follow-up scan is to be collected after the initial RECIST 1.1-defined PD, preferably at the next (and no later than the next) scheduled imaging visit, and no less than 4 weeks after the prior assessment of PD and this scan is evaluated using the Confirmation of Radiological Progression criteria are outlined in Appendix E. If the subsequent scan does not confirm the immediate prior radiological PD, scanning should continue until the next RECIST 1.1-defined PD which in turn will require a subsequent scan evaluated using the Confirmation of Radiological Progression criteria outlined in Appendix E.

Follow up of patients post discontinuation of study drug

Patients who have discontinued treatment due to toxicity or symptomatic deterioration, clinical progression, or who have commenced subsequent anticancer therapy will be followed up with tumor assessments until RECIST 1.1-defined PD plus an additional follow-up scan or until death (whichever comes first) and followed for survival.

Survival

All patients in the study should be followed up for survival.

Statistical methods

All statistical analyses will be performed by AstraZeneca or its representatives (e.g. CRO).

A comprehensive statistical analysis plan (SAP) will be prepared and finalized within 3 months of the first enrolled patient, and any subsequent amendments will be documented, with final amendments completed prior to reporting of the data.

All analyses will be descriptive in nature. Categorical (e.g., gender) study measures will be reported using frequency and proportions and continuous measures (e.g., age) will be reported using mean, median, standard deviation and range. Additionally, Kaplan-Meier curves will be presented for time-to-event outcomes such as overall and progression free survival.

All analyses will be based on the intention to treat (ITT) population consisted of all enrolled patients who had received at least 1 dose of study drug (chemotherapy or Durvalumab). For the overall study population and for any subpopulation, estimated 95% CIs for various event rates will be calculated.

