6.2 Measures to minimize bias

6.2.1 Patient enrollment

This is a single arm, open label study; no randomization or blinding will be performed.

If a patient withdraws from the study, then his/her enrolment code cannot be reused.

Investigators should keep a record (ie, the patient screening log) of patients who entered screening.

At screening/baseline (Days -28 to -1), the Investigators or suitably trained delegate will:

- Obtain signed informed consent before any study specific procedures are performed. If laboratory or imaging procedures were performed for alternate reasons prior to signing consent, these can be used for screening purposes with consent of the patient. However, all screening laboratory and imaging results must have been obtained within 28 days of inclusion.
- Obtain a unique enrollment number (E-code), through the Interactive Web Response System (IWRS). This number is the patient's unique identifier and is used to identify the patient on the electronic case report forms (eCRFs).
- Determine patient eligibility (see Sections 5.1 and 5.2)

If the patient is ineligible and not included, the IWRS should be contacted to terminate the patient in the system.

Patients will begin treatment on Day 1. Treatment should start no more than 3 working days after being included. Patients must not be included and treated unless all eligibility criteria have been met.

If a patient withdraws from participation in the study, then his or her enrollment code cannot be reused.

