9.1 Statistical hypotheses

There is no formal hypotheses in this study.

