#### 4.1.3 Definition of comparison drug exposure

Not applicable.

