#### Endpoints analyzed:

- Progression-free survival (PFS): The PFS analysis will be based on the programmatically derived RECIST 1.1 using the Investigator tumor assessments. The analysis will be performed using Kaplan Meier plots. Summaries of the number and percentage of patients experiencing a PFS event will be provided along with median PFS and its 95% confidence interval. In addition, the proportion of patients who are progression-free at 6 (PFS 6) and 12 (PFS 12) months will be presented.

A subgroup analysis may be conducted comparing PFS in the following subgroups, assuming sufficient sample size per subgroup: platinum therapy receiving (carboplatin or cisplatin), age ( $\geq 65$ ,  $< 65$ ), gender, performance status, smoking status, CNS metastasis at baseline (Yes/No) and number of chemotherapy cycles (5 or 6 cycles vs 4 or less cycles)

For each subgroup, the HR and 95% CI will be calculated by Cox regression and a log-rank test will be provided.

- Objective response rate (ORR): The ORR will be based on the programmatically derived RECIST 1.1 using the investigator tumor data. Summaries will be produced that present the number and percentage of patients with a tumor response (CR/PR). 95% CI will also be presented.

A subgroup analysis may be conducted comparing ORR in the following subgroups, assuming sufficient sample size per subgroup: platinum therapy receiving (carboplatin or cisplatin), age ( $\geq 65$ ,  $< 65$ ), gender, performance status, smoking status, CNS metastasis at baseline (Yes/No) and number of chemotherapy cycles (5 or 6 cycles vs 4 or less cycles). Results will be compared using Chi-Squared test.

- Duration of response (DoR): DoR will be analyzed using the investigator tumor data in responding patients. Descriptive data will be provided for the DoR in responding patients (continuous data), including the associated Kaplan-Meier curves. In addition, the DoR at 1 year (DoR 12) will be analyzed.

A subgroup analysis may be conducted comparing DoR in the following subgroups, assuming sufficient sample size per subgroup: platinum therapy receiving (carboplatin

or cisplatin), age ( $\geq 65$ ,  $< 65$ ), gender, performance status, smoking status, CNS metastasis at baseline (Yes/No) and number of chemotherapy cycles (5 or 6 cycles vs 4 or less cycles)

For each subgroup, the HR and 95% CI will be calculated by Cox regression and a log-rank test will be provided.

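### The protocol says the PFS subgroup hazard ratios assess consistency of treatment effect, which a single-arm study with no comparator cannot estimate

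*Protocol*

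**What the plan says.** The design is stated plainly in Protocol 6.2.1: "This is a single arm, open label study; no randomization or blinding will be performed". SAP 4.1.3, headed "Definition of comparison drug exposure", is answered as not applicable. Protocol 9.1 says "There is no formal hypotheses in this study", and the synopsis says "All analyses will be descriptive in nature".

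For PFS, Protocol 9.5.2.2 says "A subgroup analysis may be conducted comparing PFS in the following subgroups, assuming sufficient sample size per subgroup", and lists platinum agent, age, gender, performance status, smoking status and CNS metastasis. It then gives the aim: "The purpose of the subgroup analyses is to assess the consistency of treatment effect across expected prognostic and/or predictive factors". A Cox HR with 95% CI and a log-rank test follow for each subgroup.

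The OS text in the same section repeats the HR and log-rank plan without the purpose sentence. SAP 5.2.1 does likewise for PFS, DoR and OS: "For each subgroup, the HR and 95% CI will be calculated by Cox regression and a log-rank test will be provided". The SAP also adds a chi-squared test for ORR and a further factor, the number of chemotherapy cycles (five or six against four or fewer). Nowhere does it say how these contrasts should be read.

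**The concern.** Consistency of treatment effect means that the benefit of treatment over a comparator is similar at each level of a factor. Judging it needs a treatment contrast within each level. Here there is only one treatment group, so the only available contrast is between levels, for example PS 2 against PS 0-1 among treated patients. The same holds for calling a factor predictive, which is a claim about effect modification.

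Performance status shows what is at stake. The synopsis and Protocol 2.1 give limited information on PS 2 patients as a reason for the study, and the data are meant to inform health-care decisions. If the optional analysis is run and read as the protocol states, a PS 2 HR away from 1 could be taken as durvalumab working better or worse in those patients. The data cannot support either reading.

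**Working it through.** The plan gives no figure to reproduce on this point. The check is one of identifiability, followed by an illustration.

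**Identity.** Let h(A) and h(B) be the hazards that levels A and B would have without durvalumab, and θ(A) and θ(B) the treatment HRs in those levels. Under proportional hazards, the treated hazards are h(A)θ(A) and h(B)θ(B), so the single-arm subgroup HR is

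HR(B vs A) = [h(B)/h(A)] × [θ(B)/θ(A)].

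The first factor is prognosis and the second is effect modification. Only treated patients are observed, so only the product can be estimated. More patients would not separate the two.

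**Inputs for the illustration.**
- Treatment HR 0.73: the OS result of the earlier randomised trial, quoted in Protocol 4.2.
- Prognostic HR for PS 2 vs PS 0-1: not in the documents; assumed range 1.0 to 2.0.
- Alternative treatment HRs in PS 2 of 0.50 and 1.00: assumed.

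| Prognostic HR | θ in PS 0-1 | θ in PS 2 | Subgroup HR |
|---|---|---|---|
| 1.0 | 0.73 | 0.73 | 1.0 × 0.73/0.73 = 1.00 |
| 1.5 | 0.73 | 0.73 | 1.5 × 0.73/0.73 = 1.50 |
| 2.0 | 0.73 | 0.73 | 2.0 × 0.73/0.73 = 2.00 |
| 1.5 | 0.73 | 0.50 | 1.5 × 0.50/0.73 = 1.03 |
| 1.0 | 0.73 | 1.00 | 1.0 × 1.00/0.73 = 1.37 |

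In the first three rows the effect is perfectly consistent, yet the HR runs from 1.00 to 2.00. In the fourth the effect differs between levels, yet the HR is close to 1. Read backwards, an observed HR of 1.5 fits equally well with a prognostic HR of 1.0 and θ ratio 1.5/1.0 = 1.50, with 1.5 and 1.5/1.5 = 1.00, or with 2.05 and 1.5/2.05 = 0.73.

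**Factors that are not simple baseline characteristics.**
- Platinum agent is chosen by the investigator (Protocol 6.1.2.2), has different creatinine clearance thresholds for the two agents (Protocol 5.1, criterion 9), and may be switched (Protocol 8.4.5.2). Its HR is a confounded contrast between treatment components.
- Number of cycles is known only after treatment starts. On a three-weekly schedule the fifth cycle falls at about week 4 × 3 = 12, so patients in the higher group have already remained well enough to be treated until then.

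**Secondary check: a null log-rank test.** The PS 2 cap is 30% of 85, or 25.5, so take 25 patients. Assume 51 to 85 events (60% to 100% of 85). Schoenfeld power = Φ(|ln HR| × √[D p(1−p)] − 1.96), with p = 25/85.
- Between-level HR 1.5: power 0.26 (51 events) to 0.40 (85 events).
- Between-level HR 2.0: power 0.62 to 0.83.

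A non-significant test would therefore be weak evidence even that outcomes are alike, and no evidence about treatment effect.

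**The case against.** The strongest defence is that little harm is likely. The subgroup analyses are optional and conditional on enough patients, the study is declared descriptive with no hypotheses, and the purpose sentence itself mentions prognostic factors. It occurs once, in the protocol's PFS text; the OS text and the SAP do not repeat it. The synopsis already plans 95% CIs for event rates in subpopulations. All of this stands and keeps the point minor. It does not make the stated purpose achievable, and the sentence remains the only guidance on reading these HRs, since the SAP keeps the HRs and tests without withdrawing it.

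A reader might infer more than the documents support, in three ways.
- That every subgroup HR is purely prognostic, or that the interaction is zero. Not estimable is different from zero: each HR is a mixture, and a prognostic label would assume away effect modification that the data cannot exclude. It would also be wrong for platinum agent and cycle number.
- That prognostic differences will be reported as effect modification. Nothing in the plan says so. It is a possible misreading if the analyses are run and interpreted as the protocol states.
- That a PS 2 HR above 1 is already expected. The documents give no prognostic HR for PS and name no reference level.

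**Conclusion.** The concern holds for the purpose sentence in the PFS part of Protocol 9.5.2.2, which claims for the subgroup HRs a property they cannot have in this design. This conclusion rests only on the single arm and the absence of a comparator, not on any assumed number. The numerical illustration rests on proportional hazards, an assumed prognostic HR of 1.0 to 2.0, assumed treatment HRs in PS 2 of 0.50 and 1.00, and an external OS HR of 0.73; it shows that the stated reading can fail in both directions. For OS in the protocol, and for PFS, DoR and OS in the SAP, the gap is narrower: the HRs are planned with no statement of what they mean. The correction alters no endpoint, estimate or sample size, but it does alter what may be concluded from the subgroup tables.

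**What to change.** Replace the purpose sentence in Protocol 9.5.2.2 with wording such as: *to describe outcomes within subgroups; differences between levels are associations with outcome and do not estimate treatment effect or its consistency*. Drop the reference to predictive factors. Apply that association label, not a prognostic one, to every subgroup HR, name the reference level for each factor, and call the p-values nominal. Carry the same statement into the protocol OS text and SAP 5.2.1.

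Within-subgroup Kaplan-Meier medians and landmark rates with 95% CIs can be shown beside the HRs. The synopsis already provides for interval estimates of event rates in subpopulations, so the subgroup medians are the main addition.

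The cost is wording and table labels, plus a small amount of programming if the medians are added. No new data and no change in study conduct are needed.
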